Study Title: Does Stellate Ganglion Blockade (SGB) in Men Treated for Prostate Cancer Improve Hot Flashes? A Pilot Prospective Cohort Study

Study Protocol Version 3.1 11/25 2019

NCT003796195

STU#:00208657

Version 3.1

11/25/2019

PROTOCOL TITLE: Does Stellate Ganglion Blockade (SGB) in Men Treated for Prostate Cancer Improve Hot Flashes? A Pilot Prospective Cohort Study

PRINCIPAL INVESTIGATOR:

[name], MSCI

Department of Anesthesiology

[contact]

[contact]

Co-Investigator

[name], MPH

Department of Medicine, Division of Hematology & Oncology

Statistician

[name]

Department of Anesthesiology

VERSION NUMBER:

3.1

VERSION DATE:

11/25/2019

STUDY SUMMARY:

Special Population(s)	NA
Sample Size	N = 14 is the required number of enrollees who are needed to be evaluable both at baseline and 6 months for the primary outcome. Allowing for dropouts, up to 18 pts might be enrolled
Funding Source	Internal funding
type of consent to be obtained	Written
Site	Single Site
Research Related Radiation Exposure	Yes

STU#:00208657

Version 3.1

11/25/2019

1.0 OBJECTIVES:

Scope: Men with prostate cancer with or without metastatic disease treated with androgen deprivation therapy for at least 2 months, with bothersome refractory hot flashes, will be enrolled as participants in this open label clinical trial.

Aim 1: To determine the effect of stellate ganglion blockade (SGB) for reducing hot flash frequency and severity in men with prostate cancer in the 6 months following the intervention.

Aim 2: To evaluate the effect of SGB on daily hot flash (HF) interference and sleep quality.

Hypotheses: Hot flash frequency, interference and sleep quality will be improved in men following stellate ganglion blockade with local anesthetic.

2.0 BACKGROUND:

Androgen Deprivation Therapy (ADT) is a critical component of advanced prostate cancer treatment but causes numerous adverse effects including decreased bone mass, decreased muscle mass, gynecomastia, erectile dysfunction, loss of sexual desire, depression, disordered sleep, urinary symptoms, and hot flashes (HF)(1). HF are unpleasant paroxysmal episodes of flushing, sweating with vasodilation of the face, neck, and chest. These episodes can last for seconds to minutes and are often associated with night sweats, anxiety, and insomnia and have negative effects on quality of life (9).

Although the exact mechanism of HF is unclear, HF in men on ADT appear related to decreased androgen exposure (1-5). Studies confirm that 50-93% of men who receive ADT report HF (1, 3, 6). These symptoms are typically long lasting. They start within two months of ADT initiation and persist 6 months to several years after ADT discontinuation (7). One recent study showed that 27% of men on ADT reported HF as their most distressing side effect of prostate cancer treatment (8). There is considerable psychological distress associated with poorly controlled HF in men (9, 10) that has a negative impact on mental health, including feelings of decreased masculinity and the sense that one's traditional gender role is diminished. Together, these factors compound the psychological, psychosocial and psychosexual stresses of prostate cancer survivorship.

Younger and leaner men typically have more frequent and severe HF from ADT when compared to other groups, and several genetic polymorphisms are associated with a high rate of hot flashes in men on ADT, specifically, those that effect immune function, neurotransmission, vasoconstriction, and circadian rhythms (11). Because of the numerous negative effects of HF on QOL, sleep, and sexuality, HF can make patients less likely to begin hormonal therapy and can lead to the early discontinuation of ADT (7, 12) or poor treatment adherence (13).

Few trials have been done assessing treatment of HF in men with prostate cancer, and those that have been published typically show lackluster or inconsistent outcomes or an unacceptable side effect profile (6, 13-16). Testosterone supplementation is obviously contraindicated.

STU#:00208657

Version 3.1

11/25/2019

In women, pharmacological treatments (anti-depressants, anti-epileptics, anti-hypertensives), physical/behavioral treatments (e.g., acupuncture, yoga/exercise, relaxation techniques, cognitive behavioral therapy), and natural health products (e.g., black cohosh, flax, vitamin E, ginseng) have been studied for control of HF, but most have not been critically evaluated by clinical trials in men (17-19). Most medications shown to mitigate HF have their own unique side effects, or require daily compliance to maintain consistent efficacy.

Stellate ganglion blockade (SGB) with local anesthetic may be an effective treatment of HF in men on ADT, but has not been studied in any published clinical trials. The stellate ganglion is a neural structure in the anterior cervical spine region and is part of the sympathetic nervous system. It has been injected safely in the practice of pain management for more than 50 years in cases of post herpetic neuralgia (shingles), complex regional pain syndrome (CRPS) and other painful neuropathies as well as some types of cardiac dysrhythmias. We recently published a prospective, randomized, sham controlled study of SGB in women with natural or surgical menopause, in which we found a 52% decrease in moderate to very severe HF in women who underwent a single SGB with bupivacaine, a local anesthetic, as compared to a 13% decrease in women in the sham control group who underwent an injection of saline. (20).

Another controlled study of SGB in women with breast cancer on endocrine therapy confirmed considerable reductions in frequency and intensity of HF in patients who had SGB (21). Uncontrolled studies of women with breast cancer and heterogeneous populations including postmenopausal women have demonstrated improvements in the frequency and intensity of HF following SGB, with 45-90% reduction in HF frequency or intensity, for durations ranging from 4 weeks to several months (22-24). Together, this literature provides further support of the hypothesis that SGB could be beneficial to men on ADT.

The mechanism of SGB mitigation of HF in men is unclear. The effects of testosterone on prevertebral ganglia are widely variable (25). Anatomic connections between the stellate ganglion and thermoregulatory regions in the brain via third order neurons have been described (26). SGB interrupts the sympathetic nervous system and may modulate norepinephrine levels in these thermoregulatory regions. Androgen deprivation as in ADT appears to change NE levels and activate the sympathetic nervous system in rat models (27), but the detailed interaction between testosterone and NE levels in humans is unclear (25, 28, 29). Some authors have alternatively hypothesized that Nerve Growth Factor (NGF) levels are modulated following SGB (30, 31), and there is evidence that NGF levels may decrease with testosterone withdrawal, affecting neural growth and neural plasticity (32, 33) that could ultimately effect thermoregulation.

We are currently studying SGB effects in postmenopausal women in a sham-controlled clinical trial funded by the National Institute on Aging (NIA R01AG049924-01; PI [name]).

Given the frequency and severity and interference of HF in men on ADT for prostate cancer, in addition to the negative effects HF impose on this patient population and a paucity of effective treatments, finding alternative treatments for HF in this population is needed.

STU#:00208657

Version 3.1

11/25/2019

3.0 STUDY ENDPOINTS:

Primary Outcome

Change in frequency of weekly hot flashes by self-report hot flash diary between baseline and 3 months following the intervention.

Secondary Outcomes

1. Change in frequency of weekly hot flashes by self-report hot flash diary between baseline and 1 month following the intervention.
2. Change in frequency of weekly hot flashes by self-report hot flash diary between baseline and 6 months following the intervention.
3. the change in hot flash severity (hot flash frequency * hot flash intensity) between baseline and 1, 3, 6 months following the intervention
4. the change in Hot Flash Related Daily Interference Scale (HFRDIS) between baseline and 1, 3, 6 months following the intervention
5. PROMIS SF4a (sleep)
6. Patient Global Impression of Change Score (PGIC)
7. Number and type of adverse events related to SGB according to NCI-CTCAE v5.0.

Mean frequency= $((F_{mi}+F_{mo}+F_{se})/7)$

where F_{mi} , F_{mo} and F_{se} are the weekly total number of mild, moderate or severe/very severe HF events

Mean severity = $(F_{mi}+2\times F_{mo}+3\times F_{se})/7$

where F_{mi} , F_{mo} and F_{se} are the weekly total number of mild, moderate or severe/very severe HF events In the case of mean severity, frequency of mild vasomotor symptoms (VMS) is not counted at baseline

4.0 STUDY INTERVENTION:

Image Guided Right Sided Stellate Ganglion Block with 0.5% Bupivacaine

5.0 PROCEDURES INVOLVED:

5.1 Study design:

We aim to conduct a single-site, open label trial of SGB in men with prostate cancer on ADT.

5.2 Methods & Study Procedures:

Refer to the Section 5.3, Schedule of Events, for additional information.

Visit 1

Consent

After participants have reviewed and signed the consent form in person, they will be interviewed to determine candidacy for the study. They will be asked to provide information about themselves and their medical history. Participants will consult with [name] who will explain the injection procedure and perform a brief physical examination (focus on cervical range of motion and anterior cervical anatomy) to confirm patient eligibility for the

[name], MD STU00208657

V 3.1 11/25/2019

STU#:00208657

Version 3.1

11/25/2019

study. The SGB will be scheduled within 2 weeks of this visit, based on convenience and availability of the participant. Participants will be asked to complete a Hot Flash Related Daily Interference Scale and secondary outcome measures at this visit. They will complete a hot flash diary for at least 1 week. To qualify for study inclusion, participants must have ≥ 28 hot flashes per week or will be considered a screen failure and will be excluded.

Visit 2

Intervention

Participants will be NPO for 6 hours prior to the intervention and will arrange transportation home. At the time of the injection procedure, an angiocatheter will be placed in the hand/arm for peripheral intravenous access as a safety precaution. Participants will be positioned supine in cervical extension on a procedure table in the fluoroscopy suite of the NMH Pain Clinic (Lavin 1400). The anterior neck will be prepped with chlorhexidine and draped in the standard sterile manner.

A right-sided SGB will be performed. Using fluoroscopic guidance, the C6 vertebra will be identified and the skin overlying the tubercle will be anesthetized using 2 mL of 1% lidocaine. Using digital pressure to laterally retract the carotid artery, a 22 g 1.5-inch needle will be placed to make contact with the anterolateral portion of the C6 vertebra and then retracted 1-2 mm and secured; contrast material (iopamidol 1-2 mL) will be injected with fluoroscopic guidance to confirm contrast dye spread in the prevertebral fascial plane and to rule out intravascular or intrathecal dye spread. 0.5% bupivacaine (5 mL) will be injected and the needle will be removed.

Monitoring after SGB

Participants will be transferred to a recovery area and monitored in a reclining position for approximately 20-30 minutes after the SGB to assess potential adverse effects of the injection. Vital signs will be measured approximately every 5 minutes during the recovery phase. Presence of a Horner's sign (miosis, ptosis, anhydrosis) will be recorded and will validate successful SGB. Expected adverse events and serious adverse events may include any of the following:

Adverse Events (Immediate Post-Procedure):

Local anesthetic toxicity (seizure, loss of consciousness)

Inability to swallow (superior laryngeal nerve spread of local anesthetic)

Difficulty with phonation (recurrent laryngeal nerve spread of local anesthetic)

Weakness of arm (brachial plexus spread of local anesthetic)

Weakness of arms and legs (epidural spread of local anesthetic)

Shortness of breath (phrenic nerve spread of local anesthetic)

These effects would be clinically apparent in the Post-Anesthesia Care Unit (PACU) during the 30 minute post injection observation period; patients are not discharged until vital signs, motor and sensory function of the upper and lower extremities are assessed as normal, and patient is able to phonate and swallow liquids.

STU#:00208657

Version 3.1

11/25/2019

Follow-Up

- 24h follow-up (+3 days to allow for scheduling constraints with weekends)

Participants will be contacted one day following the intervention to assess for any adverse events or side effects. Expected adverse events may include any of the following:

Pain at injection site

Swelling at injection site

Severe bruising at injection site

- Long-term follow-up at 1, 3, and 6 months

Participants will complete daily hot flash diaries and weekly HFRDIS scales via REDcap email for the duration of the 6 month follow up. Secondary measures will be collected at 1, 3 and 6 months after the intervention. Participants will have the opportunity to share any new concerns or problems with research personnel during these interactions, and will be instructed to contact [name] (PI) if any more urgent concerns arise. Contact information is provided in the ICF.

Patients will be contacted via telephone or via REDcap generated email on a weekly basis, if needed, to encourage continued participation in follow up measures, and data will be collected via REDcap. Reminder phone calls will be made if the participant forgets to send their information.

Schedule of Events

	Screening and Baseline Assessments ⁷	Registration ⁷	Day of Intervention ⁸	1 day follow-up (+ 3 day window)	1 month follow-up (± 7 day window)	3 month follow-up (± 7 day window)	6 month follow-up (± 7 day window)
Informed consent	X						
Demographic information and medical history ¹	X						
Physical exam, height, and weight ²	X						
AE assessment ³	X		X	X	X		
HF severity assessments ⁵	X (collect HF data for ≥ 1 week prior to the day of intervention)				X	X	X
HFRDIS ⁶	X			Weekly during follow-up per Section 5.2			
PROMIS SF4a ⁶	X				X	X	X
PGIC score ⁶					X	X	X
Registration ⁷		X					
SGB Intervention ⁸			X				
Horner's sign assessment post-SGC intervention ⁸			X				
Timed vitals during recovery ⁹			X				
Follow-up contact ¹⁰				X	X	X	X
Weekly reminders ¹¹				X			
Hot flash diary ^{12, 5}				X			

STU#:00208657

Version 3.1

11/25/2019

1. Demographic information and medical history to include: age, body mass index, race, years of education, marital status, Gleason score, duration of hot flashes (months), type of ADT (specify) per Section 5.4. Height and weight to be collected for BMI calculation. Pathology report to be collected to determine Gleason Score.
2. Brief physician-directed physical exam to focus on cervical range of motion and anterior cervical anatomy per Section 5.2.
3. Refer to Section 5.6 for details on the collection of AEs and SAEs. In brief, AEs that are related to the intervention (irrespective of expectedness) will be collected from the time of consent (baseline) through the 30 days after the intervention (the 1 month follow-up visit). All SAEs (irrespective of attribution/relatedness or expectedness) will be collected from the time of consent (baseline) through 30 days after the intervention (the 1 month follow-up visit).
4. Screening labs not required for this study; not a standard of care
5. Patient-reported hot flash (HF) frequency and HF intensity to be collected, based on the participant's hot flash diary. These values will be used to calculate a HF severity score, per Section 3.0. Participants must complete the diary for at least 1 week prior to receipt of the intervention to be able to determine the baseline HF severity score.
6. HFRDIS, PROMIS SF4a, and PGIC score questionnaires to be administered via REDCap. Other methods may also be used (i.e. in person, over the phone, through mail or email, etc.) if required.
7. All screening assessments to be conducted 0-14 days prior to registration, unless otherwise indicated. Participants must register to the trial prior to receipt of the study intervention. Refer to Section 12.0 for registration instructions.
8. The SGB intervention should take place AFTER registration and within 1-2 weeks after the baseline/screening assessments per Section 5.2. Participants are to complete the diary daily starting at least 1 week prior to receipt of the SGB intervention. Details of the SGB intervention and Horner's sign assessment are described in Section 5.2
9. Vitals are to be assessed approximately every 5 minutes for approximately 20-30 minutes while participants are in recovery, after receipt of SGB.
10. Participants will be contacted for follow-up via their preferred method of contact (phone call, in-person visit, email, etc.) 1 day and 1 month after the intervention to collect AE/SAE data. They will also be contacted (via REDcap or other means) at 1 month, 3 months, and 6 months to collect information for secondary outcomes.
11. Qualified research staff may contact participants via their preferred method of contact (phone call, in-person visit, email, REDcap generated email, etc.) approximately once a week (or less frequently as needed) throughout the course of the study to remind participants to comply with study procedures, including but not limited to: scheduling appointments; completing the HF diary; completing the HFRDIS, PROMIS SF4a, and PGIC score questionnaires; assessing AEs/SAEs.
12. Participants will be instructed to begin completing the hot flash diary at the time of screening/baseline assessments. Participants are to complete the diary daily starting at least 1 week prior to receipt of the SGB intervention and through the 6-month follow-up time point. Weekly phone calls (or other preferred method of contact) may be used to remind participants to comply.

STU#:00208657

Version 3.1

11/25/2019

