17.0 STATISTICS, DATA MANAGEMENT AND CONFIDENTIALITY

Power Analysis

We derived our sample size estimates for the analysis of the primary endpoint for this study, i.e., change in weekly frequency of severe hot flashes at 6 months post-intervention vs. baseline (pre-intervention), based on data in the literature from a randomized controlled trial comparing different treatments for HF in men with prostate cancer on ADT. The pre-treatment baseline weekly frequency of severe hot flashes was assumed to be 46.0 ± 43 (mean \pm SD)³⁵.

Because there are no published data on the variability of within-person differences between the 6-month and baseline measures for severe hot flashes, we estimated the variance for this 6-month change variable using the equation for the variance of the difference between two possibly correlated measurements, as provided in the textbook by Rosner, 7th edition, pg. 305. This equation depends on the baseline standard deviation (SD1), the standard deviation of the 6-month assessment (SD2), and the within-person correlation (ρ) between the baseline and 6 month follow-up variables. We allowed the original baseline and 6-month SDs to differ at the two assessment times but varied the within-person correlation between pre- and 6-month post-treatment measurements (range: $\rho = 0.5$ to $\rho = 0.8$, in increments of 0.1).

The results below assumed a value of 21 for SD2 and assume the properties of the exponential distribution are approximately valid for the severe hot flashes measure (i.e., we assumed that the underlying mean and standard deviation are approximately equal).

Using a paired one-sample t-test comparing changes between 6-month assessment and baseline, a sample size of 14 participants will provide 80% power with a two-sided $\alpha = 0.05$ to detect a reduction of 52% in mean frequency of severe hot flashes ($\Delta = 23.9$) if $\rho = 0.8$ (e.g., from a mean of 46.0 at baseline to 22.1 at 6-months following treatment)²⁰. As an exploratory calculation, if our assumptions were revised to $\rho = 0.7$, then the corresponding sample size required would be 17 participants.

If we expect up to about 20% attrition in studies such as this, then we will recruit up to a total of 18 participants in this pilot study.

Statistical Plan

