Nominal patient characteristics data will be summarized descriptively as number and percent of participants in each category. Ordinal and continuous patient data that are not approximately normally distributed will be summarized as median and interquartile range (IQR). Normally distributed continuous patient data will be presented as mean \pm SD.

STU#:00208657

Version 3.1

11/25/2019

Data required for the primary outcome variable, i.e., mean daily frequency of severe hot flashes in the study sample at 6 months after the intervention vs. the baseline daily frequency of hot flashes in the study sample, will be reported as the mean \pm SD if appropriate, or as the median (IQR) otherwise. The primary outcome data will be evaluated using a paired t-test if the data are approximately normally distributed, or using with the Wilcoxon matched pairs signed rank test if they are not. The mean difference and 95% CI will be calculated. The criterion for rejection of the null hypothesis (i.e. no change over the baseline to 6-month follow-up assessment of the mean weekly frequency of severe hot flashes) will be a two-tailed $p < 0.05$.

For AE analysis, safety and tolerability will be summarized descriptively by providing the frequency of adverse events by severity, type, and attribution.

Differences from baseline and associated 95% CIs will be calculated for planned analyses. Variables that are approximately normally distributed (e.g., hot flash frequency) will be summarized as mean \pm SD. These data at baseline, 1, 3, and 6 months will be compared using the one-way repeated measures analysis of variance with pairwise multiple comparison with baseline made using the Holm-Sidak method when appropriate.

The criterion for rejection of the null hypothesis for all of the secondary analyses will be a two-tailed $P < 0.05$, as this is an exploratory study.

With severe HF frequency selected as the primary outcome, $> 35\%$ reduction from baseline to 6 months will be considered to be clinically significant. However, as this is an exploratory study, a larger reduction was used for the power analysis presented above.

If this study shows meaningful treatment effects in this study population, we plan to further evaluate our hypotheses in a larger, randomized blinded sham controlled study.

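### The protocol names two primary endpoints (hot flashes of any grade at 3 months; severe hot flashes at 6 months), and the N = 14, 80% power claim belongs only to the second.

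*Combined protocol and SAP*

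**What the plan says.** Section 3.0 (Study Endpoints) gives the primary outcome as "Change in frequency of weekly hot flashes by self-report hot flash diary between baseline and 3 months following the intervention". It sets no severity limit. Its formula for mean frequency sums three terms, which "are the weekly total number of mild, moderate or severe/very severe HF events", and divides by 7. Secondary outcome 2 in the same list is "Change in frequency of weekly hot flashes by self-report hot flash diary between baseline and 6 months following the intervention". A frequency endpoint restricted to severe events does not appear in that list.

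Section 17.0 (Power Analysis) identifies the primary endpoint as "change in weekly frequency of severe hot flashes at 6 months post-intervention vs. baseline (pre-intervention" and states on that basis that "a sample size of 14 participants will provide 80% power". Its Statistical Plan describes the primary variable as "mean daily frequency of severe hot flashes in the study sample at 6 months after the intervention", and the null hypothesis as "no change over the baseline to 6-month follow-up assessment of the mean weekly frequency of severe hot flashes". The threshold for clinical significance, a reduction of more than 35%, is also set for severe hot flashes at 6 months.

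The Study Summary ties the 14 evaluable participants to baseline and 6 months but names no severity class. Aim 1 in Section 1.0 refers to the whole 6 months after the intervention, so it picks out neither endpoint.

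**The concern.** A reader who goes to the endpoints section and a reader who goes to the statistics section come away with different primary endpoints. The conflict has two dimensions, the events counted and the time point, and it is hard to read as a single slip: Section 3.0 separately places the 6-month change among the secondary outcomes, while Section 17.0 repeats severe and 6 months in several places.

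Two things are at stake. First, in an open-label single-arm study with follow-up at 1, 3 and 6 months, leaving the primary open allows the more favourable result to be given that label after the data are seen. The plan says meaningful effects would lead to a sham-controlled trial, so the label has consequences. Second, the power statement could be attached to an endpoint for which it was never calculated. The Section 3.0 primary has no power calculation, no clinical threshold and no evaluability rule at 3 months.

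**Working it through.** **1. The two definitions side by side**

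| Element | Section 3.0 | Section 17.0 |
|---|---|---|
| Events counted | All grades (no restriction; formula sums mild, moderate, severe/very severe) | Severe |
| Time point | 3 months | 6 months |
| Status of the 6-month change | Secondary outcome 2 (no severity restriction) | Primary (severe) |
| Unit | Weekly in words; formula divides by 7 | Weekly in the power analysis and null hypothesis; daily in the description of the primary variable |
| Primary test and rejection rule | None given | Paired t-test or Wilcoxon signed rank, two-tailed p < 0.05 |
| Power and threshold | None given | N = 14 for 80% power; reduction of more than 35% |

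The term all grades is a reading of the unrestricted wording and the formula; the document does not use it. Frequency at 3 months is compared with baseline in Section 17.0, through a repeated-measures analysis of variance with Holm-Sidak comparisons, but that is not the test assigned to the primary outcome.

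**2. Reproducing the plan's sample size**

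Inputs, all from the Section 17.0 Power Analysis and all for severe hot flashes at baseline and 6 months: baseline mean 46.0 per week, SD1 = 43, SD2 = 21, correlation 0.8, reduction 52%, two-sided alpha 0.05.

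- Difference: 0.52 × 46.0 = 23.92, stated as 23.9.
- SD of the paired difference: √(SD1² + SD2² − 2ρ·SD1·SD2) = √(43² + 21² − 2 × 0.8 × 43 × 21) = √845.2 = 29.07.
- Paired t-test power (noncentral t, n − 1 degrees of freedom, noncentrality 23.9/29.07 × √n): n = 13 gives 77.7%, n = 14 gives 81.1%. The smallest n reaching 80% is 14, as stated.
- At correlation 0.7: SD = √1025.8 = 32.03; n = 16 gives 79.7%, n = 17 gives 82.3%. The plan's alternative of 17 also reproduces.
- Attrition: 14/(1 − 0.20) = 17.5, rounded up to 18, as stated.

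The arithmetic is sound.

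**3. The same calculation for the Section 3.0 primary**

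It cannot be done. The document gives no mean, SD, correlation or expected effect for all-grade frequency at 3 months. Purely as an illustration, assume the severe, 6-month difference and SDs carried over unchanged. Over the plan's own correlation range:

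| ρ | SD of difference | Power at n = 14 | n for 80% |
|---|---|---|---|
| 0.8 | 29.07 | 81% | 14 |
| 0.7 | 32.03 | 73% | 17 |
| 0.6 | 34.73 | 66% | 19 |
| 0.5 | 37.24 | 60% | 22 |

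Nothing in the document supports that assumption for the other endpoint.

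**4. Smaller inconsistencies in the same definition**

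- Unit: 23.9 per week is 23.9/7 = 3.4 per day. Used consistently at both visits, the factor of 7 changes the reported estimate but not the p-value.
- Baseline class: the Statistical Plan sets severe events "at 6 months after the intervention vs. the baseline daily frequency of hot flashes", leaving out the severity restriction at baseline. This is probably a dropped word. Read literally, it would compare severe events at follow-up with all events at baseline and so exaggerate any reduction.

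**The case against.** The strongest reply is that the document leans one way. The Study Summary and every statement of the primary in Section 17.0 agree on 6 months, and Section 17.0 is consistent that severe events are primary at follow-up. Only one primary test and rejection rule is written down, so there are two primary labels but one primary analysis, and Section 3.0 may simply be out of step. Diaries cover both time points, so no data are lost, and the study is a small exploratory pilot.

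Much of this is fair. It limits the practical harm and makes the correction cheap. It does not settle the conflict: no precedence rule is stated, the Study Summary is silent on severity, and Section 3.0 is where a reader looks for the primary outcome. Whether the two endpoints would lead to different conclusions is unknown.

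A second fair point is that reproducing N = 14 for severe hot flashes at 6 months does not make that figure secure. It holds at correlation 0.8 only. Section 2.0 reports the 52% effect for moderate to very severe hot flashes in women, a class that matches neither definition exactly. The power analysis assumes a roughly exponential measure, while the Statistical Plan provides a rank test for non-normal data. These qualify the power claim for the Section 17.0 endpoint and lend none to the Section 3.0 endpoint.

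**Conclusion.** The concern holds. The plan is wrong as written: it has two primary endpoints that differ in event class and time point, and no text reconciles them. The N = 14, 80% power statement reproduces (81.1%) for severe hot flashes at 6 months under the plan's inputs, including correlation 0.8. It says nothing about all-grade frequency at 3 months, whose power cannot be determined from the document. The damage is to the primary label and the power attribution, not to data collection. The conclusion rests on the current text of both sections and on reading the unrestricted Section 3.0 wording and formula as covering all grades. The time-point conflict stands even without that reading. This must be fixed before follow-up data are examined.

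**What to change.** State one primary endpoint, with event class, time point and unit, and with the same class at baseline and follow-up, in identical terms in the Study Summary, Section 3.0 and Section 17.0. List the other as secondary. Do this before follow-up data are examined.

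- **If severe at 6 months is chosen:** the stated N and power remain attached to it, conditional on correlation 0.8. Acknowledge that the 52% effect came from moderate to very severe events and that the entry rule of 28 hot flashes per week has no severity limit. Add a rule for deriving weekly severe counts. Section 3.0 names the quantity, but the diary in Section 5.4 grades intensity only while awake, counts night sweats without grading them, and defines its grades partly by episode counts (severe is 5 or more).
- **If all-grade at 3 months is chosen:** rewrite the primary test, null hypothesis, evaluability rule and clinical threshold for it, and state that the N = 14, 80% figure does not apply.
- **Either way:** use one unit throughout, say whether night sweats count, and restore the matching event class at baseline in the Statistical Plan.

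The cost is a wording amendment and a matching update wherever the endpoint is recorded. The severe endpoint may also need a diary change if the form in use does not record counts by grade; the form is not in the document. The all-grade endpoint gives up the stated power figure, and the N it would need is unknown until inputs are supplied.
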